8 ASSESSMENT OF SAFETY

8.1 SPECIFICATION OF SAFETY PARAMETERS

8.1.1 DEFINITION OF ADVERSE EVENTS (AE)

For the purposes of this treatment protocol, an adverse event (AE) is any untoward medical occurrence associated with the use of an intervention in humans, whether or not considered intervention-related (21 CFR 312.32 (a)).

Progression of the patient's lung disease, or events which are unequivocally due to disease progression, should not be reported as an AE (unless it is considered to be related to the investigational product by the treating physician).

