6.1.2. OTHER SAFETY CONSIDERATIONS

Physical examinations (by PI, sub-I or clinical team) will be performed at baseline, following IV infusion (as clinically indicated by the clinical team), and daily during hospitalization. Patient will have a follow-up visit at Day 28 (+/-2 days) and 90 days after Day 1 of investigational product administration. Data analysis will commence at 28 days. Follow up at 90 days will be to assess for any delayed SAEs. Please see table of events for details. The baseline and end of treatment (or termination) examination will be a complete physical examination; other examinations should be focused, at the discretion of the treating physician, to assess changes from the previous examination.

Other safety assessments will include vital signs and oxygen requirement. The treating physician will review all vital sign results and oxygenation parameters, and clinically significant findings will be reported as AEs and followed or treated according to institutional guidelines or the treating physician's medical judgment.

Any immediate hypersensitivity reaction after infusion will result in discontinuation of treatment.

Confidential Page **21** of **32**

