7 TREATMENT VISIT SCHEDULE

Evaluation	Baseline (within 3 days)	Infusion Days ⁱ	Day 4	Day 7 (+ 1 day)	Day 14 (+ 2 days)	Day 28 (+2 days) -	Day 90 (+ 5 days)
Informed Consent	Х						
Medical History, height, weight, and Demographics	х						
Physical Exam	Х	Xj	Х	Х			
Vital Signs ^a	Χ	X ^{bj}					
Hematology ^c	Х		Х	X*		X*	
Serum Chemistry d	Х	X*	Χ*	X*		X*	
Coagulation ^e	Х		X*			X*	
Pregnancy Test ^f	Х						
EKG	X*						
Urinalysis	X*						
HLA Typing	Х						
PRA	Х					Х	
Donor screening panel	Х						
COVID PCR	Х		Χ*	X*		X*	
Chest x-ray	Х*		Χ*	X*		X*	
ABG	Х	Xgj	Χ*	X*		X*	
Pre-medications		Χj					
Concomitant Meds	X	X	Х	X		Х	
Adverse Events Assessment		X	Х	X			Х
Lung Injury Severity Score (Murray)	х	Xı	Х	Х	X	Х	

LAR

Confidential Page 22 of 33

hCT-MSC Infusion		Xh					
PaO2/FiO2	Х	Xj	Х	Х	X		
Prone Ventilation ^k	Х	Х	X	Х			
Neuromuscular				X			
blocker ^k	X	X	X				
Inhaled nitric acid ^k	Х	Х	X	Х			
Inhaled				X			
epoprostenaol ^k	X	X	X				
Corticosteroids ^k	X	X	X	X			
Survival						X	Х
Oxygen use							X ^m

- a. Blood Pressure, Heart Rate, Respiratory Rate, Temperature, and O₂ Saturation
- b. Vitals are taken prior to pre-medications, prior to infusion, every 15 minutes during infusion, every 30 minutes post infusion X 2, then hourly X 4.
- c. Hematology: Hemoglobin, Hematocrit, platelet count, White Blood Cells, and differential
- d. Chemistry: CRP, ESR, AST, ALT, LDH, total bilirubin, alkaline phosphatase, total protein, albumin, sodium, potassium, chloride, carbon dioxide, calcium, blood urea nitrogen, creatinine, creatinine clearance, glucose
- e. Coagulation: Prothrombin Time (PT)/aPTT/INR, D-dimer
- f. Pregnancy Test (WOCBP) Women of Child Bearing Potential. If done prior to baseline as part of hospitalization, this does not need to be repeated.
- g. ABGs to be done prior to infusion, and 1-4 hours after each infusion
- h. Three infusions will be given on days 1, 2 and 3.
- i. All Days will be calculated from the first infusion, or Day 1.
- j. These elements will be done on Day 1, Day 2, and Day 3. Premedications, and vital signs will also be done at each infusion. Physical exams will be done daily during hospitalization and data will be pulled from those clinical notes.
- k. Monitor the use, duration, and if applicable, the dose during hospitalization
- I. Only SAEs are gathered at Day 90
- m. If use of oxygen is required at Day 90 will be documented
- n. Day 28 is the time the primary endpoint will be evaluated.

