8.3 TIME PERIOD AND FREQUENCY FOR EVENT ASSESSMENT AND FOLLOW-UP

The occurrence of an AE or SAE may come to the attention of the treating physician during patient visits or any other times the patient requires medical care. Information to be collected includes event description, time of onset, clinician's assessment of severity, relationship to investigational product (assessed only by those with the training and authority to make a diagnosis), and time of resolution/stabilization of the event. All AEs will be followed to adequate resolution.

Any condition present before the first treatment/infusion, including pre-existing conditions and pretreatment protocol AEs, will be considered medical history and will not be reported as a treatmentemergent AE unless the condition worsens during or after infusion. Any worsening (i.e., any clinically significant adverse change in frequency and/or intensity) of a preexisting condition, which is temporally associated with the use of the investigational agent, is also an AE.

Changes in the severity of an AE will be documented to allow an assessment of the duration of the event at each level of severity to be performed. AEs characterized as intermittent require documentation of onset and duration of each episode.

Patients will be followed daily while in hospital and for 7 days after administration of infusion. In addition, patients will be followed up to 90 days after administration for severe adverse events and survival. However, data analysis will be conducted at 30 days for purposes of publication and dissemination of information.

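### Respiratory worsening read as ARDS progression is an AE under 6.1.1, 6.1.2 and 8.3 but not under 8.1.1, and 9.4 has no attribution-free table that would show it

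*Combined protocol and SAP*

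**What the plan says.** Four places in the protocol govern whether a fall in oxygenation is recorded as an adverse event.

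- **Section 6.1.2:** "The treating physician will review all vital sign results and oxygenation parameters, and clinically significant findings will be reported as AEs". There is no exception for disease progression.
- **Section 6.1.1:** the same instruction is given for laboratory results, and blood gases are listed in that section.
- **Section 8.3:** a clinically significant worsening "of a preexisting condition, which is temporally associated with the use of the investigational agent, is also an AE".
- **Section 8.1.1:** the opening definition covers "any untoward medical occurrence associated with the use of an intervention in humans, whether or not considered intervention-related". The next paragraph takes out progression of the lung disease and "events which are unequivocally due to disease progression, should not be reported as an AE". By its own terms this exclusion holds only "unless it is considered to be related to the investigational product by the treating physician".

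Three further places decide what happens to the event afterwards. Section 8.2.2 asks for a causality grade on the AEs that have been collected. Section 3.3 defines the later-reactions part of the primary endpoint by attribution to the product. Section 9.4 names infusion-related reactions and other unexpected product-related reactions as the events to tabulate.

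On measurement, note g to the visit schedule in section 7 reads "ABGs to be done prior to infusion, and 1-4 hours after each infusion". The infusion-day entry does not carry the asterisk that marks tests taken only from standard care.

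**The concern.** Inclusion criterion 5 requires ARDS, so in this trial worsening oxygenation is both the expected course of the disease and a plausible form of harm from an intravenous cell product. Section 3.6.1 itself lists bronchospasm among the observed reactions. The recording rule therefore matters most for respiratory events, and there the sections disagree.

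Two things are at stake. First, the AE record may differ between sites for the same clinical event. An event left out under 8.1.1 also leaves no causality grade that anyone could re-examine. Second, even a consistent AE record would not bring unattributed respiratory events into the planned safety analysis, because that analysis is built on attribution. Phase II is randomised and blinded, so a comparison by arm could show an excess that judgement on single patients cannot. The plan does not specify that comparison.

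**Working it through.** **1. One event under each rule.** Take a patient whose PaO2/FiO2 falls to a clinically significant degree after the second infusion and who is then intubated.

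| Rule | Physician reads it as progression | Physician considers it product-related |
|---|---|---|
| 6.1.1, laboratory findings | AE | AE |
| 6.1.2, oxygenation findings | AE | AE |
| 8.1.1, general definition | AE | AE |
| 8.1.1, progression exclusion | Not an AE | AE, through the exception |
| 8.3, worsening of a pre-existing condition | AE if temporally associated | AE if temporally associated |

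The rules agree in the right-hand column and conflict in the left. No section gives an order of precedence. The exception in 8.1.1 does not settle the matter, because it makes recording depend on attribution while the other rules require recording whatever the cause.

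**2. Following the unrecorded event.** If 8.1.1 is applied, the event is not collected and 8.2.2 assigns it no causality grade. It does not enter the later-reactions endpoint in 3.3 or the reactions named in 9.4.

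**3. Following the recorded event.** If 6.1.2 is applied, the event is collected and graded, say as unlikely or unrelated. It still does not enter the later-reactions endpoint or the named 9.4 tabulation, because both require attribution. Reconciling the definitions therefore repairs the record but leaves the analysis unchanged.

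**4. The plan's own safety figure.** Section 9.1.1 gives the chance of at least one product-related reaction in 10 patients as 0.65, 0.94 and 0.98 for rates of 0.10, 0.25 and 0.33. The formula is 1 − (1 − p)^10, which gives 0.651, 0.944 and 0.982. The table reproduces.

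**5. Illustration of dependence on attribution.** Assume that a share m of true product reactions is read as progression and not reported. The documents give no value for m, so a range is shown. The formula becomes 1 − (1 − p(1 − m))^10. For p = 0.10 and m = 0.50 this is 1 − 0.95^10 = 0.401.

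| Rate p | m = 0 | m = 0.25 | m = 0.50 | m = 0.75 |
|---|---|---|---|---|
| 0.10 | 0.651 | 0.541 | 0.401 | 0.224 |
| 0.25 | 0.944 | 0.875 | 0.737 | 0.476 |
| 0.33 | 0.982 | 0.942 | 0.835 | 0.577 |

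This shows how strongly detection depends on attribution. It does not estimate the effect of the conflict between sections.

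**6. Data available for a by-arm table.** With 20 patients per pooled arm and 3 infusions each, the schedule allows at most 20 × 3 = 60 before-and-after pairs per arm. This is the amount of data available, not a measure of bias. The pairs within a patient are not independent.

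**The case against.** The case for leaving the plan alone has real substance.

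- **Wording of 8.1.1.** It says that events should not be reported, requires the link to be unequivocal for events due to progression, and restores anything the physician considers product-related. This narrows the exclusion. Progression of the lung disease itself, however, carries no such qualifier.
- **Acute reactions are covered.** Section 5.3 names wheezing, breathlessness, cough and a pulse oximetry reading under 90 as infusion-related reactions, and vital signs are taken every 15 minutes during the infusion. Bronchospasm recognised as a reaction would count. This stands, and it confines the point to worsening read as progression.
- **Other data remain.** PaO2/FiO2, Murray score, ventilator-free days and mortality are collected. Section 6.1 names oxygenation as a safety measure, the SAE definition has no progression exclusion of its own, and the first stopping rule counts deaths within 24 hours whether related or not. So it would be wrong to say that oxygenation has no place in the safety evaluation. What is missing is a specified comparison across each infusion. The closing sentence of 9.4 on other outcomes is too general to supply one.
- **The DSMB charter is not available here**, so what the board will see cannot be judged.

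A reader might draw two stronger conclusions that the documents do not support.

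- **That the contradiction by itself biases the primary endpoint.** Step 3 shows otherwise. An event the physician attributes to the product is reportable under either rule, and an event not so attributed stays outside the later-reactions component even when recorded.
- **That Phase I shows unrecorded events**, because section 3.6 lists only four SAEs, all deaths. That section is a short background summary, not an AE listing. The deaths were judged unrelated and were reported all the same. They fell on days 7, 27, 39 and 344, none within 24 hours of the Day 1 to 3 infusions. Phase I was also open label, so it says nothing about blinded attribution.

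**Conclusion.** The point stands in limited form. The sections conflict on whether a non-fatal respiratory worsening read as progression is an AE, and nothing resolves the conflict in a population that all has ARDS. The consequence is an AE record that can differ between sites and lacks a causality grade for events left out. Separately, the planned safety tabulation depends on attribution and specifies no comparison across infusions, although the blood gases for one are scheduled.

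The size cannot be calculated. The documents give neither the frequency of such events nor the share read as progression, and the range in step 5 rests on an assumed share. The conclusion itself rests only on the wording of the sections and on the ARDS entry criterion. It is worth correcting because safety is the primary objective and the remedy uses data already scheduled.

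**What to change.** 1. Reconcile 6.1.1, 6.1.2, 8.1.1 and 8.3 into one recording rule applied alike in all arms. Respiratory worsening after an infusion should be recorded whatever its presumed cause, with causality entered as a separate item.
2. In 9.4, add a descriptive Phase II table comparing pooled hCT-MSC with placebo. It should show recorded respiratory worsening after infusion irrespective of attribution and, for each infusion, the change in PaO2/FiO2 from before to 1–4 hours after. Give the number of patients with both values at each infusion, since some will not receive all three.
3. State that FiO2 is recorded with each of these blood gases. The schedule lists PaO2/FiO2 on infusion days but does not tie it to both draws.
4. Supply the table to the DSMB.

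Any clinical threshold for calling a change significant is for the sponsor to set.

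The cost is wording in five sections and one table. The downside is more disease-related AE entries in both arms. With at most 20 patients per pooled arm the table can only describe, which matches the stated approach to Phase II.

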8.1.2. DEFINITION OF SERIOUS ADVERSE EVENTS (SAE)

For the purposes of this treatment protocol, a "serious" adverse event is defined in regulatory terminology as any untoward medical occurrence that:

- 1. Results in death.
- 2. Is life-threatening.

The patient was at risk of death at the time of the event; it does not refer to an event that hypothetically might have caused death if it were more severe.

- 3. Requires in-patient hospitalization or prolongation of existing hospitalization. Note: Hospitalization (including hospitalization for an elective procedure) for a pre-existing condition which has not worsened does not constitute a serious adverse event.
- 4. Results in persistent or significant disability or incapacity.
- 5. Is a congenital anomaly/birth defect
- 6. Is an important medical event

Any event that does not meet the above criteria, but that in the judgment of the treating physician jeopardizes the patient, may be considered for reporting as a serious adverse event. The event may require medical or surgical intervention to prevent one of the outcomes listed in the definition of "Serious Adverse Event".

8.2 CLASSIFICATION OF AN ADVERSE EVENT

8.2.1 GRADING OF ADVERSE EVENT

For the purposes of this treatment protocol, all adverse events will be graded according to the NCI Common Terminology Criteria for Adverse Events (CTCAE) version 5.0. The CTCAE v5.0 is available at https://ctep.cancer.gov/protocoldevelopment/electronic_applications/ctc.htm#ctc_40

8.2.2 RELATIONSHIP TO INVESTIGATIONAL AGENT

For all collected AEs, the treating physician will evaluate the patient to determine the AE's causality based on temporal relationship and his/her clinical judgment using the following categories:

- Definite The AE is *clearly* related to the treatment protocol.
- Probable The AE is *likely* related to the treatment protocol.
- Possible The AE may be related to the treatment protocol.
- Unlikely The AE is doubtfully related to the treatment protocol.
- Unrelated The AE is clearly *NOT* related to the treatment protocol.

8.2.3 EXPECTEDNESS

Expected events are those that have been previously identified as resulting from administration of the investigational agent. An adverse event is considered unexpected, for expedited reporting purposes only, when either the type of event or the severity of the event is not listed in the current Product Label.

8.3 TIME PERIOD AND FREQUENCY FOR EVENT ASSESSMENT AND FOLLOW-UP

The occurrence of an AE or SAE may come to the attention of the treating physician during patient visits or any other times the patient requires medical care. Information to be collected includes event description, time of onset, clinician's assessment of severity, relationship to investigational product (assessed only by those with the training and authority to make a diagnosis), and time of resolution/stabilization of the event. All AEs will be followed to adequate resolution.

Any condition present before the first treatment/infusion, including pre-existing conditions and pretreatment protocol AEs, will be considered medical history and will not be reported as a treatmentemergent AE unless the condition worsens during or after infusion. Any worsening (i.e., any clinically significant adverse change in frequency and/or intensity) of a preexisting condition, which is temporally associated with the use of the investigational agent, is also an AE.

Changes in the severity of an AE will be documented to allow an assessment of the duration of the event at each level of severity to be performed. AEs characterized as intermittent require documentation of onset and duration of each episode.

Patients will be followed daily while in hospital and for 7 days after administration of infusion. In addition, patients will be followed up to 90 days after administration for severe adverse events and survival. However, data analysis will be conducted at 30 days for purposes of publication and dissemination of information.

8.3.1 ADVERSE EVENT REPORTING

The Institutional Review Board (IRB) of record must be notified of AE's according to its policies.

8.3.2 SERIOUS ADVERSE EVENT REPORTING

Unexpected serious suspected adverse reactions will be reported to FDA on an expedited basis as per 21 CFR 312.32.

8.4 STOPPING RULES

The safety monitoring committee will consider stopping the trial if any one of the following events occur:

- 1. Three deaths occur within 24 hours of MSC infusion (related or unrelated to study product)
- 2. One Severe or Life-Threatening infusion-related reaction
- 3. One death related to study product
- 4. One case of graft versus host disease

9 STATISTICAL CONSIDERATIONS

9.1 SAMPLE SIZE JUSTIFICATION

This study will enroll and treat 10 patients with MSCs for the first, open label portion of the study.

The primary objective is to evaluate safety of this treatment in COVID-19 related ARDS. If safety is demonstrated, an additional 40 patients will be enrolled and randomized to hCT-MSC or placebo for the purpose of evaluating the potential benefit of hCT-MSC in COVID-19 related ARDS.

9.1.1 PHASE I

The first phase of the study is uncontrolled and the sample size is intended to support evaluation of safety. Therefore, as an alternative to power calculation we provide the following estimates of the probability of observing different types of product-related adverse reactions among the first 10 enrolled patients based on binomial probabilities.

With 10 patients enrolled and treated our study will have the following probability of identifying product-related adverse reactions that happen in 10%, 25% and 33% of infusions. These calculations show that even with 10 patients our study is likely to identify the most commonly occurring product- related adverse reactions.

Background Rate of Product-Related	Probability of Observing >= 1 Reaction
Reaction	in 10 Patients
0.10	0.65
0.25	0.94
.33	0.98

9.1.2 PHASE II

The second phase of the study will randomize 20 patients to placebo and 20 to hCT-MSC. The primary utility of the randomized phase of the trial is to evaluate the feasibility of conducting a larger, randomized trial comparing hCT-MSC to placebo, and to conduct descriptive analyses of efficacy outcomes. To enroll and randomize 90% of the eligible patients screened is a positive indicator of feasibility. The primary efficacy outcome of interest is time to recovery, defined as discharge from the hospital (alive) or remaining in the hospital without the need for supplemental oxygen or other COVID-related medical care. We expect based on previous research that 30% of patients in the placebo arm will recover at Day 28. This study is not powered to detect differences between arms except when those differences are large. Therefore, the approach to analysis will be descriptive. For example, with 20 patients per arm and no losses to follow-up, a 365-day accrual period and 28 days of follow-up per patient, the study would have 54% power to detect a doubling in the hazard of recovery with treatment (hazard ratio = 2.0) and 76% power to detect a hazard ratio of 2.5 using a log-rank test with 2-sided Type I error of 5%.

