2. PROTOCOL SYNOPSIS

This is a 50 patient, Phase 1/2a multi-center pilot study to test the safety and to describe the preliminary efficacy of intravenous administration of allogenic human cord tissue mesenchymal stromal cells (hCT- MSC) as an investigational agent, under U.S. INDs 19968 (Duke) and 19937 (U Miami) to patients with acute respiratory distress syndrome (ARDS) due to COVID-19 infection (COVID-ARDS). Patients will be eligible for treatment with 3 daily consecutive doses of hCT-MSC at 1 million cells/kg (max dose 100 million cells) in the phase 1 portion of the study or a fixed dose of 100 million cells daily x 3 days, 12-36 hours apart in the phase 2 portion of the study, if they have a

Confidential Page 8 of 32

confirmed diagnosis of COVID-19 and meet clinical and radiographic criteria for ARDS. The primary endpoint is short-term safety of hCT-MSC infusions given on this schedule. The key secondary endpoints are 28 day survival, an increase in PaO2/FiO2 ratio by 50% at 96 hours, days to hospital discharge to home or rehab, and number of days requiring mechanical or non-invasive ventilation or high flow nasal cannula.

The study will be executed in two phases. The first 10 consecutive patients will all receive investigational product. The second part of the study is a randomized, controlled trial in 40 additional patients. The overall aim of the study is to establish safety and to gain critical information as to whether patients with COVID-ARDS will benefit from MSC infusions. Results from the first 10 patients will be compared with concurrent outcomes utilizing standard of care treatments in participating hospitals and in published reports in the medical literature. Results from the additional 40 patients will be analyzed as a randomized placebo control trial. The trial is relying on focused eligibility of the participants (patients with ARDS), single cohort with short trial time (4 weeks), and simple assessment of clinical outcome (survival, improvement of ARDS). This is a sequential design in the sense that after the first 10 patients are evaluated a decision will be made by the PIs and the Data Safety Monitoring Board whether to proceed with the exploratory randomized portion of the study.

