9.2 RANDOMIZATION PLAN

In Phase II of this study, a total of 40 participants will be randomized in a ratio of 2:1:1 to placebo, hCT-MSC manufactured at Duke, or hCT-MSC manufactured at Miami. This randomization plan will yield 20 participants on placebo and 10 in each of the hCT-MSC arms. The two hCT-MSC arms will be pooled for analyses comparing treated patients to placebo (see below). The infusion will be blinded so that the medical teams and the patients/LARs will not know which product (placebo, Duke MSC or Miami MSC) the patient receives. There will be unblinded technicians in the laboratories preparing the cells and placebo for infusion, but the final product configuration will be the same for all infusions.

Phase I, Safety 10 patients 1x10^6/kg patient weight (max 100x10^6) Phase II Randomization, Efficacy Placebo hCT-MSCs 10 patients DUKE Fixed dose 100x10^6 10 patients UNIVERSITY OF MIAMI Fixed dose 100x10^6

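### Phase II power is overstated: 28 days of follow-up per patient gives about 28% at HR 2.0 and 48% at HR 2.5, not 54% and 76%

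*Combined protocol and SAP*

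**What the plan says.** Section 9.1.2 sets the size of the randomized phase: "The second phase of the study will randomize 20 patients to placebo and 20 to hCT-MSC". Section 9.2 reaches the same 20 versus 20 by pooling two cell-product arms of 10 each. The main efficacy outcome is time to recovery, and the planning assumption is that "30% of patients in the placebo arm will recover at Day 28".

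The power example assumes "with 20 patients per arm and no losses to follow-up, a 365-day accrual period and 28 days of follow-up per patient". With a log-rank test at two-sided 5%, it concludes that "the study would have 54% power to detect a doubling in the hazard of recovery with treatment (hazard ratio = 2.0) and 76% power" at a hazard ratio of 2.5.

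Other sections also point to a horizon of about four weeks:

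- The synopsis (section 2) describes a "single cohort with short trial time (4 weeks").
- Section 6.1.2 starts the data analysis at 28 days; section 8.3 says 30 days.
- The section 7 footnotes limit the Day 90 contact to survival, SAEs and whether oxygen is still needed.

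Section 9.1.2 also says that the study can detect only large differences, that the analysis will be descriptive, and that the power figures are an example.

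**The concern.** Log-rank power depends on the number of events. With 30% recovery on placebo and a 28-day limit on each patient, 40 patients cannot supply many recoveries, so 54% and 76% look too high. The 365-day accrual term is a second sign of trouble. If every patient is followed for the same 28 days without losses, the speed of enrolment cannot affect power, yet it is listed as an input.

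These are the only figures in the plan that say what the randomized efficacy comparison could detect, so they define what counts as a large difference. A reader would take it that a true hazard ratio of 2.5 would be detected about three times in four, and might read a flat Kaplan-Meier comparison as fair evidence against such an effect.

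**Working it through.** **Inputs (all from section 9.1.2).** 20 per arm; placebo recovery 30% by Day 28; no losses; 28 days per patient; 365-day accrual; HR 2.0 and 2.5; log-rank, two-sided 5%. A constant hazard is assumed where a hazard is needed: λ = −ln(0.70)/28 = 0.01274 per day.

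**Formula.** Schoenfeld power with equal arms is Φ(½·√D·ln HR − 1.96), where D is the expected number of recoveries in both arms.

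**Step 1: reproduce the stated figures.** Assume uniform accrual over A = 365 days, then F = 28 more days, with everyone followed to a common end (28 to 393 days each). The average recovery probability at hazard h is 1 − [exp(−hF) − exp(−h(A+F))]/(A·h).

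- Placebo: 0.851. Treated: 0.947 (HR 2.0) or 0.965 (HR 2.5).
- D = 20 × (0.851 + 0.947) = 36.0, or 20 × (0.851 + 0.965) = 36.3.

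| Method, common cut-off | HR 2.0 | HR 2.5 |
|---|---|---|
| Stated | 54% | 76% |
| Lakatos | 53.0% | 75.8% |
| Schoenfeld | 54.7% | 78.8% |
| Freedman | 51.6% | 73.3% |
| Simulation, 20,000 runs | 52.0% | 76.1% |

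This reading matches the stated pair: Lakatos and simulation are within 2 points of both values.

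**Step 2: apply the inputs as written, 28 days per patient.** Under proportional hazards the treated recovery by Day 28 is 1 − 0.7^HR.

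- HR 2.0: 1 − 0.7² = 0.51, so D = 20 × (0.30 + 0.51) = 16.2. Power = Φ(½ × 4.025 × 0.693 − 1.96) = Φ(−0.565) = 28.6%.
- HR 2.5: 1 − 0.7^2.5 = 0.59, so D = 20 × (0.30 + 0.59) = 17.8. Power = Φ(½ × 4.219 × 0.916 − 1.96) = Φ(−0.027) = 48.9%.

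| Method, fixed 28 days | HR 2.0 | HR 2.5 |
|---|---|---|
| Schoenfeld | 28.6% | 48.9% |
| Lakatos | 27.8% | 47.1% |
| Freedman | 26.8% | 44.0% |
| Simulation, 20,000 runs | 27.8% | 47.9% |

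The simulated type I error at fixed 28 days was 5.1%, so the test itself behaves properly.

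**Step 3: events the stated power would need.** D = 4(1.96 + z)²/(ln HR)², where z is the normal quantile of the stated power.

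- 54% at HR 2.0: 4 × (1.96 + 0.100)²/0.480 ≈ 35.
- 76% at HR 2.5: 4 × (1.96 + 0.706)²/0.840 ≈ 34.

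The design supplies about half of these.

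**Step 4: try other readings (Schoenfeld).**

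| Reading | HR 2.0 | HR 2.5 |
|---|---|---|
| One-sided test, 28 days | 40.1% | 61.3% |
| 30% taken as not recovered, 28 days | 50.3% | 74.9% |
| 30 days per patient | 29.8% | 50.8% |
| 90 days per patient | 49.6% | 74.3% |

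None of these gives both stated values.

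**Step 5: what the design can detect.** Solving the step 2 expression for HR, 54% power needs HR of about 2.6, 76% about 3.3 and 80% about 3.5. At HR 3.5, for example, 0.7^3.5 = 0.287, D = 20 × (1.3 − 0.287) = 20.3, and power is about 80%.

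**Step 6: plausibility of the long-follow-up reading.** It needs 20 × 0.851 = 17.0 placebo recoveries. The synopsis gives mortality of 30–60% for this condition; at 30%, at most 20 × 0.70 = 14 placebo patients could recover.

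**The case against.** The strongest reply concerns consequence. Safety is the primary endpoint, and section 9.1.2 gives feasibility and description as the purpose of Phase II. It presents the power figures as an example and already calls the study underpowered for anything but large effects. The analysis plan in section 9.4 specifies Kaplan-Meier plots and descriptive statistics, with no log-rank test and no success threshold. The only stated indicator for a larger trial is randomizing 90% of eligible screened patients. All of this stands: the power figures set neither the sample size nor any decision rule, and any harm from over-reading them is a possibility, not something the plan builds in.

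A second reply is that outside the power sentence no section fixes a censoring day for time to recovery. Days to discharge has no cap, examinations continue daily in hospital, and oxygen need is recorded at Day 90. That is fair, and the size of the overstatement does depend on the horizon. But 28 days per patient is the sentence's own input, and even complete recovery follow-up to Day 90 stays below both printed values.

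Finally, the common cut-off explanation is an inference from how well it fits; the documents do not say how the power was computed. The finding does not depend on it.

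**Conclusion.** The stated power does not follow from the stated design. With 28 days per patient it is about 27–29% at HR 2.0 and 44–49% at HR 2.5. By Schoenfeld the overstatement is 54 − 28.6 = 25 points and 76 − 48.9 = 27 points; by Freedman it is 27 and 32 points. At HR 2.0 the printed figure is nearly double the recomputed one, and at HR 2.5 the chance of detection is a little under one in two.

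The result assumes proportional hazards, 30% placebo recovery and no losses. The constant-hazard assumption matters little, because the Schoenfeld and Freedman figures at a fixed horizon depend only on the Day 28 recovery proportions. The likely cause is that 28 days was entered as follow-up after the last enrolment instead of follow-up per patient. The plan's conclusion that Phase II is underpowered remains true; it is more underpowered than stated.

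**What to change.** In section 9.1.2, replace the power sentence with figures for fixed 28-day follow-up:

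- about 16 expected recoveries and about 28% power at HR 2.0;
- about 18 expected recoveries and about 48% power at HR 2.5;
- 80% power only at HR of about 3.5.

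Name the formula or software used. Delete the 365-day accrual term, or state that it does not affect power when follow-up per patient is fixed. State the day on which time to recovery is censored, and reconcile the 28-day and 30-day analysis times in sections 6.1.2 and 8.3. If a longer recovery horizon was intended, say so, schedule the data collection and recompute.

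Keep the sample size and the descriptive framing. The cost is a wording change and a less favourable power statement; no patients are added.
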